# 9.6.6 Electrocardiograms

Standard 12-lead ECG recordings will be obtained within 60 minutes pre-dialysis at screening/baseline, at the EOT visit (Day 15), and at the EOS visit (Day 29); see **Table 1**. ECG

recordings must be performed after the subject has been resting in a supine position for at least 5 minutes, and prior to other procedures scheduled at that same time (e.g., blood draws).

The Principal Investigator must review, interpret sign, and date all ECG tracings. ECG abnormalities must be documented on the CRF and assessed for clinical significance. All treatment-emergent clinically significant ECG abnormalities must be reported as AEs.

Paper copies of ECG tracings will be kept as part of the subject's file at the site.

# 9.6.7 Assessment of Dialysis Adequacy (Kt/V)

Kt/V is a standard measure of dialysis adequacy, where *K* stands for the dialyzer urea clearance, *t* stands for the duration of the dialysis session, and *V* stands for the volume of urea distribution (roughly corresponding to the volume of water contained in the patient's body).

As part of the safety evaluations, Kt/V will be measured at EOT (Day 15), and compared to the baseline value, which will be calculated as the average of the last three pre-study Kt/V values obtained as part of the subject's standard of care. In case the Kt/V value obtained at EOT is reduced compared to baseline (pre-study measurements), the Investigator will determine (in consultation with the Medical Monitor, as needed) if the event qualifies for reporting as an AE.

# 9.6.8 Laboratory, Biomarker, and PK Samples

The assessments listed in this section will be performed at Covance Central Laboratory Services (Covance). Instruction manuals and supply kits will be provided by Covance for all central laboratory assessments.

An overview of the standard safety laboratory, biomarker, and PK sampling requirements is provided below. For additional details on laboratory assessments and sample handling, refer to the laboratory manual.

# 9.6.8.1 Safety Laboratory Assessments

Samples for the following safety laboratory tests will be sent to the central laboratory for analysis:

- Hematology panel: red blood cell (RBC) count, hemoglobin, hematocrit, and white blood cell (WBC) count, with differential (neutrophils, eosinophils, lymphocytes, monocytes, basophils, and other cells), if clinically indicated.
- Complete Metabolic Panel (CMP):
  - o Glucose, albumin, total protein;
  - Electrolytes: sodium, potassium, bicarbonate, chloride, calcium, magnesium, phosphate;
  - o Renal function tests: blood urea nitrogen (BUN), creatinine;
  - Liver function tests: (ALT, AST, bilirubin), and
  - Lipid profile: total cholesterol, low-density lipoprotein (LDL) cholesterol, high-density lipoprotein (HDL) cholesterol, and triglycerides (TG).
- Coagulation panel includes: partial thromboplastin time (PTT), INR, and platelet count.

All blood sampling will occur pre-dialysis (at the time of needle placement).

In addition, all subjects will undergo the following tests at screening only:

- Serology for:
  - HIV
  - HBV: hepatitis B "e" antigen (HBeAg) and PCR for the active virus (HBV deoxyribonucleic acid [DNA]); and
  - o HCV: HCV antibody and PCR for active virus (HCV ribonucleic acid [RNA])
- For women of child bearing potential only: serum beta-human chorionic gonadotropin (β-hCG) pregnancy test (the results of the screening pregnancy test must be negative for enrolment).

The schedule for laboratory assessments is provided in **Table 1**. All baseline laboratory assessments may occur during screening (within 7 days prior to the first dose of the study drug).

The total volume of blood drawn from each subject for safety laboratory assessment will be approximately 57 mL over the course of the study. Instructions for safety laboratory specimen collection, handling, and shipping will be included in the laboratory manual provided by the Central Laboratory (Covance).

#### 9.6.8.2 Biomarker Assessments

Blood samples will be obtained for biomarker evaluation according to the schedule in **Table 1** and **Table 4**. Serially collected blood samples will be processed to obtain plasma for the determination of the following biomarkers:

• Uncarboxylated MGP; uncarboxylated osteocalcin; Activated Protein C, PIVKA-II protein; Fetuin A, osteoprotegerin, *hs*-CRP, and Time to Formation of Secondary Calciprotein Particles (T-50 Test); including CPP size.

Blood sampling for biomarker analysis will always occur pre-dialysis (at the time of needle placement): on Day 1 (Baseline), Day 15 (EOT), and Day 22 (1 week after the last study drug dose).

The total volume of blood drawn from each subject for biomarkers assessment will be approximately 48 mL over the course of the study (approximately 16 mL per assessment time-point). Instructions for biomarker specimen collection, handling, and shipping will be included in the laboratory manual provided by the Central Laboratory (Covance).

Blood

Sample **Biomarkers Type Timing** Day 1, pre-dialysis\* Uncarboxylated MGP; unccarboxylated osteocalcin, Blood Activated Protein C, PIVKA-II protein, Fetuin A, (Week 1, Baseline) osteoprotegerin, hs-CRP, and Time to Formation of Secondary Calciprotein Particles (T-50 Test); including CPP Blood Day 15, pre-dialysis\* Uncarboxylated MGP; unccarboxylated osteocalcin, Activated Protein C. PIVKA-II protein, Fetuin A. (EOT) osteoprotegerin, hs-CRP, and Time to Formation of

Secondary Calciprotein Particles (T-50 Test); including CPP

Secondary Calciprotein Particles (T-50 Test); including CPP

Uncarboxylated MGP; unccarboxylated osteocalcin, Activated Protein C, PIVKA-II protein, Fetuin A,

osteoprotegerin, hs-CRP, and Time to Formation of

 Table 4
 Biomarker Assessments

CPP=calciprotein particles; EOT=end-of-treatment; hs-CRP= high-sensitivity C-Reactive Protein; MGP=matrix gamma-carboxyglutamic acid (Gla) protein; PIVKA-II=Protein Induced in Vitamin K Absence/Antagonist-II; T-50=Time to Formation of Secondary Calciprotein Particles.

size.

size.

Day 22, pre-dialysis\*

(1 week after the last

study drug dose)

#### 9.6.8.3 Pharmacokinetic Assessments

Blood for PK assessments will be sampled as follows:

- On Visit 1/Day 1 (baseline) and Visit 4/Day 8 (Week 2, on-treatment): pre-dialysis (at the time of needle placement; denoted as 0 hours), followed by study drug administration, and then at 1 hour (+/- 5 minutes), 2 hours (+/- 5 minutes), 3 hours (+/- 5 minutes), 4 hours (+/- 30 minutes)/before needle removal, 6 hours (+/- 30 minutes), 8 hours (+/- 30 minutes), and 24 hours (+/- 60 minutes) after study drug administration;
- On Visit 2/Day 3, Visit 3/Day 5, Visit 5/Day 10, Visit 6/Day 12, and Visit 7/Day 15: pre-dialysis
  (at the time of needle placement, at 0 hours), immediately followed by study drug
  administration, and then at 4 hours (+/- 30 minutes)/ before needle removal; and
- On Visit 8/Day 17 (Week 3, off-treatment): pre-dialysis only (at the time of needle placement).

The timing and sequence of PK blood sample collections relative to the study drug administrations and dialysis will be as follows:

- PK samples taken pre-dialysis (pre-dose; at 0 hour): Samples will be collected after needle
  placement and will be immediately followed by the study drug administration. Immediately
  following drug administration, dialysis is to be started.
- PK samples taken during dialysis (post-dose): Samples will be collected at 1 hour (+/- 5 minutes), 2 hours (+/- 5 minutes) and 3 hours (+/- 5 minutes) after the 0-hour PK time-point.

[figure not shown]
\* Pre-dialysis=at the time of needle placement

- PK samples taken post-dialysis (post-dose): Samples will be collected when the dialysis is completed (before needle removal) or at 4 hours (+/- 30 minutes) after the 0-hour PK timepoint, whichever occurs first.
- Note: The duration of dialysis sessions is expected to be approximately 4 hours; however, the
  actual duration should not have an impact on the PK sample collection time-points.

The calendar date and actual clock time will be recorded for each PK blood sample collection and the actual elapsed time from dosing will be used for the PK calculations.

Refer to Figure 5 for further details.

Figure 5 - Sequence of PK Sampling, Visits 1 - 8

Plasma samples will be assayed for EPN-701 concentrations (ng/mL) according to standard procedures, using a validated high-performance liquid chromatography (HPLC) tandem mass spectrometric (LC/MS/MS) method.

Apart from the plasma concentrations at each time-point, depending on the observed levels, the following PK parameters may also be determined:

- Maximum plasma concentration (Cmax) [ng/mL]
- Time to maximum plasma concentration (Tmax) [hr]
- Area under the concentration-time curve (AUC) from time 0 to 24 hours (AUC0-24 [hr×ng/mL]).

The total volume of blood drawn from each subject for PK assessment will be approximately 108 mL over the course of the study (approximately 4 mL per assessment time-point). Instructions for PK specimen collection, handling, and shipping will be included in the laboratory manual provided by the Central Laboratory (Covance).

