# 6.1.2 Long-Active Derivatives of Vitamin K2: Therapeutic role for Menaquinone-7

EPN-701 is a new formulation containing highly purified menaguinone-7 (MK-7) that belongs to the vitamin K2 family of compounds. Subject to approval by the FDA, EPN-701 would be the first and only drug approved for the orphan indication Calciphylaxis (also referred to as Calcific Uremic Arteriolopathy [CUA]), specifically to address peripheral soft tissue calcification and related calcification of the medial smooth muscle cells of the vasculature present in most ESRD patients. Menaguinones have a common functional naphthoguinone ring system (also shared with phylloquinone) and an unsaturated polyisoprenyl side chain. They are designated based on the length of the aliphatic side chains attached to the naphthoguinone ring (Booth and Suttie, 1998; Shearer and Newman, 2008). Menaquinone nomenclature is based on the number of isoprenoid units, and ranges from 1 to 15 (e.g., MK-7 for the vitamer with a side chain consisting of 7 isoprenoid units) (Marles et al. 2017). The chemical structure of MK-4 and MK-7 compared to phylloquinone (vitamin K1) is presented in Figure 4. Although both phylloquinones and menaguinones are fat-soluble, their lipophilicity increases substantially at increasing chain length. Thus, when compared to MK-4, MK-7 has high lipid solubility, greater tissue concentration and longer plasma half-life. While MK-7 and MK-4 are both well absorbed in humans, the plasma levels of MK-7 are significantly higher due to its longer half-life of 72 hours. In contrast, MK-4 has a half-life of approximately 3 hours (Schurgers and Vermeer, 2002; Schurgers et al. 2007c).

Dietary sources of menaquinones include chicken, egg yolk, dairy products, cow liver, and fermented foods such as cheese, yogurt, sauerkraut, and natto, a traditional Japanese food made from soybeans fermented with *Bacillus subtilis varnatto* (Schurgers et al. 2007c; Marles et al. 2017).

The naphthoquinone ring system shared by phylloquinones (vitamin K1) and menaquinones MK-4 and MK-7 (vitamin K2). The designation of MK-4 versus MK-7 is dependent upon the length of the aliphatic side chains attached to the naphthoquinone ring.

In addition, there are more than 200 dietary supplement products containing MK-7 currently on the market in the United States, the majority of which have a manufacturer's suggested MK-7 dose of 50 µg/d (NIH DSLD 2016). The Acceptable Daily Intake is 120 µg/day (FDA 2012).

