## 6.2.3 Clinical Pharmacokinetics of EPN-701

The current EPN-701-001 study will be the first investigation of the pharmacokinetics (PK) of EPN-701 in humans. Published clinical PK data for MK-7 is available in the literature.

In a study comparing the pharmacokinetic profile and the efficacy of MK-7 and vitamin K1, in healthy volunteers, maximum serum concentrations of MK-7 were seen approximately 4 hours after intake, followed by a steep decline in serum concentrations and then a second phase at 8-96 hours in which MK-7 remained stable for up to 4 days or more. MK-7 was shown to have a much longer half-life than vitamin K1 (68 hours vs 1-2 hours). Both MK-7 and vitamin K1 showed linear dose-response curves at 4 hours post treatment, from 0 to 500  $\mu$ g; however, at 24 hours, MK-7 at 100  $\mu$ g gave an upper limit of normal range for total serum vitamin K (1  $\mu$ g/L), whereas there was no effect of vitamin K1 at up to 200  $\mu$ g. MK-7 accumulated during the first two weeks until it reached a plateau level of approximately 6  $\mu$ g/L (Schurgers et al. 2007c).

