## **Exploratory Objectives:**

- To determine the PK profile of EPN-701 in subjects with ESRD on stable hemodialysis.
- To determine, in subjects with ESRD on stable hemodialysis, the plasma levels of the following biomarkers after two weeks of EPN-701 treatment relative to baseline:
  - Osteoprotegerin
  - o Fetuin A
  - o High-sensitivity C-Reactive Protein (hs-CRP).
  - o Time to Formation of Secondary Calciprotein Particles (T-50 Test); including CPP size.

Specific objectives and corresponding endpoints for the study are outlined (in Table 2) below.

Table 2 Study Objectives and Corresponding Endpoints

Objectives	Corresponding Endpoints		
Primary Objectives:			
Safety:  • To determine the safety and tolerability of EPN-701 (administered for two weeks at a daily dose of 10 mg) in subjects with ESRD on stable hemodialysis.	Primary Safety Endpoint:  Frequency of treatment-emergent adverse events (AEs) and treatment-emergent AEs assessed as related to the study drug (defined as possibly, probably, and definitely related events). A treatment-emergent AE is defined as any AE with an onset between the first dose of the study drug and the last study visit, or any AE with an onset prior to the first dose that increases in severity or frequency after the first dose of study drug. Adverse events include both clinical events and laboratory abnormalities that are assessed as clinically significant.  Secondary Safety Endpoints:  Frequency of serious adverse events (SAEs), AEs		
Secondary Objectives:	leading to study drug discontinuation, and AEs of special interest (AESI).  Changes from baseline in laboratory parameters Changes from baseline in ECG parameters		
, , , , , , , , , , , , , , , , , , ,			
To determine, in subjects with ESRD on stable hemodialysis, the plasma levels of the following biomarkers after two weeks of EPN-701 treatment relative to baseline: uncarboxylated MGP; uncarboxylated osteocalcin; Activated Protein C; and PIVKA-II protein.	Biomarker Endpoints:  Biomarker ratios on Day 15 (end-of-treatment) and Day 22 compared to baseline:  Ratio of uncarboxylated to total MGP  Ratio of carboxylated to uncarboxylated osteocalcin  Ratio of carboxylated to uncarboxylated Protein C  Plasma levels of the following biomarkers on Day 15 (end-of-treatment) and Day 22 compared to baseline:  Uncarboxylated MGP  Uncarboxylated osteocalcin  Activated Protein C  PIVKA-II protein		

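### Off-drug PK sampling ends about one half-life after the last dose, and the Day 22 biomarker sample has no concentration paired with it

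*Combined protocol and SAP*

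**What the plan says.** The exploratory PK objective in Section 7 is "To determine the PK profile of EPN-701 in subjects with ESRD on stable hemodialysis". Section 9.6.8.3 and Table 1 schedule full 0-24 h profiles on Days 1 and 8, samples at 0 h and 4 h on Days 3, 5, 10, 12 and 15, and one last tube: "On Visit 8/Day 17 (Week 3, off-treatment): pre-dialysis only (at the time of needle placement". The parameters in Sections 9.6.8.3 and 11.7 are Cmax, Tmax and AUC0-24, all optional.

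On kinetics, Section 6.1.2 says "the plasma levels of MK-7 are significantly higher due to its longer half-life of 72 hours", and Section 6.2.3 says "MK-7 was shown to have a much longer half-life than vitamin K1 (68 hours vs 1-2 hours". Section 6.2.3 also describes "a second phase at 8-96 hours in which MK-7 remained stable for up to 4 days or more", and reports that "MK-7 accumulated during the first two weeks until it reached a plateau level".

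Section 9.6.8.2 puts the biomarker samples on "Day 1 (Baseline), Day 15 (EOT), and Day 22 (1 week after the last study drug dose"). Table 1 also has pre-dialysis safety blood on Days 22 and 29, with no PK tube on either day.

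**The concern.** A drug with a half-life near three days is followed for about three days after dosing stops. This is the first PK study of EPN-701 in humans, it is done in dialysis patients, and Section 6.2.5 acknowledges that the dose is above those in earlier MK-7 trials. The published half-life therefore cannot be taken for granted here.

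Two things depend on how quickly the drug leaves. The first is how to read the Day 22 secondary biomarkers: whether a change from Day 15 reflects falling exposure cannot be judged without a concentration from the same draw. The second is how much exposure remains during follow-up to Day 29. Once subjects have finished, these samples cannot be recovered.

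**Working it through.** **1. The plan's own figure.** Samples per subject: 8 (Day 1) + 8 (Day 8) + 5 × 2 (Days 3, 5, 10, 12, 15) + 1 (Day 17) = 27. At 4 mL each, 27 × 4 = 108 mL, which matches Section 9.6.8.3. No PK draw after Day 17 has been overlooked.

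**2. Inputs.** Half-life (t½) 68 h (Section 6.2.3) and 72 h (Section 6.1.2); 14 daily doses, Days 1 to 14 (Section 9.3.5 and Table 1). Residual log-SD per sample is assumed to be 0.2 (about 20%), with a range of 0.1 to 0.3, because the documents give none.

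**3. Off-drug window.** Fraction left = 2^(−h/t½), with h counted from a Day 14 dose.

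| Day | h | Half-lives (68 h / 72 h) | Left |
|---|---|---|---|
| 17 | 72 | 1.06 / 1.00 | 48% / 50% |
| 22 | 192 | 2.82 / 2.67 | 14% / 16% |
| 29 | 360 | 5.29 / 5.00 | 2.5% / 3.1% |

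The off-drug samples fall at about 24, 28 and 72 h. That is a span of 48 h, or 0.67-0.71 half-lives, and all three lie inside the 8-96 h phase that Section 6.2.3 calls stable. Day 22 would be the first sample beyond it.

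**4. Precision of one subject's elimination rate, off-drug samples only.** k = ln 2 / t½ = 0.01019 per h (68 h) or 0.00963 per h (72 h). SE(k) = 0.2 / √Sxx, where Sxx is the sum of squared deviations of the sample times from their mean.

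- 24, 28, 72 h: Sxx = 1,419; SE = 0.00531; CV = 52% / 55%.
- Adding 192 h: Sxx = 18,444; SE = 0.00147; CV = 14% / 15%.
- Adding 192 and 360 h: Sxx = 81,613; SE = 0.00070; CV = 7% / 7%.

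**5. Accumulation.** Share of plateau after n doses = 1 − 2^(−24n/t½). The 24 h samples after the Day 1 and Day 8 doses and the pre-dose samples on Days 3, 5, 8, 10, 12 and 15 are troughs after 1, 2, 4, 7, 8, 9, 11 and 14 doses. They run from 21-22% to 96-97% of plateau, so the rise is observed. The Day 8 profile sits at 84-86%.

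**6. Precision using the troughs as well.** Under a mono-exponential model, the concentration h hours after dose n is A·e^(−kh)·(1 − e^(−24kn)) / (1 − e^(−24k)). Fitting A and k on the log scale to the seven earlier troughs plus the three off-drug samples gives, from the information matrix:

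| Samples | CV of k, log-SD 0.2 | Log-SD 0.1 to 0.3 |
|---|---|---|
| As planned | 18-19% | 9-28% |
| Plus Day 22 | 9-10% | 5-15% |
| Plus Days 22 and 29 | about 5% | 2.5-8% |

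**7. Day 15 dosing.** The synopsis, Table 1 note 14 and Section 9.6.8.3 have drug given straight after the Day 15 pre-dialysis sample. Section 9.3.5 and Table 1 (dosing row and note 13) stop at Day 14, and Section 9.5.2 lists dosing at Visits 1 and 4 but not Visit 7. Counting Day 22 as one week after the last dose, and Day 29 as two weeks after, points to Day 15. With a Day 15 dose, Day 17 would be 48 h later: 0.67-0.71 half-lives, with 61-63% left. Day 22 would be 168 h later, with 18-20% left.

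**The case against.** The strongest reply is that the plan delivers what it promises. PK is exploratory, Cmax, Tmax and AUC0-24 on Days 1 and 8 can be obtained from this schedule, and no half-life is promised. The analyses are descriptive over 15 subjects. Residual error alone in a group mean is 52-55% / √15 = 13-14% from the off-drug samples, or about 5% with the troughs (18-19% / √15), before between-subject variation. All of this stands, and it is why the point is an improvement and not a defect.

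Three stronger readings are tempting, and the documents do not support them:

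- **Accumulation is hardly measured.** Eight trough times through Day 15, plus 4 h samples near the published peak time, trace it. What is missing is a full profile at the end of dosing.
- **A subject's elimination rate cannot be estimated.** That follows only if the troughs are ignored. With them, the CV is 18-19% under the same simple model.
- **Day 8 is passed off as steady state.** No section says so; Section 9.6.8.3 labels it only as on-treatment in Week 2. Moving that profile to Day 12 would need a Saturday draw and would compare a Friday profile with a Monday one, at a different point in the dialysis week. It is not recommended.

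A further caution concerns Day 29. Its gain requires a level near 2.5-3% of the end-of-dosing value to be quantifiable above dietary MK-7. Section 9.4.2 prohibits no foods, and no assay limit is given.

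**Conclusion.** The point holds as a limitation of the design. Off-drug sampling covers about one half-life, and the Day 22 secondary biomarkers have no matching concentration. A Day 22 tube roughly halves the CV of an individual elimination rate when the troughs are used (18-19% to 9-10%), and cuts it to under a third when they are not (52-55% to 14-15%).

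The figures assume mono-exponential decline, a Day 14 last dose, independent residual error of 20%, and published half-lives not measured for EPN-701 at this dose in dialysis patients. The biphasic decline described in Section 6.2.3 weakens the mono-exponential assumption, and with it the trough-based figures in particular. The direction of the result is the same across residual log-SDs of 0.1 to 0.3.

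**What to change.** - In Section 9.6.8.3, Table 1 and the synopsis, add one 4 mL PK tube to the pre-dialysis draw already scheduled on Day 22. Add one on Day 29 as well if levels are expected to be quantifiable above the Day 1 pre-dose value.
- In Section 11.7, add an elimination half-life estimated from all troughs and off-drug samples, using actual times since dose.
- Restate the PK blood volume as 28 × 4 = 112 mL, or 29 × 4 = 116 mL with Day 29.
- Reconcile the passages that end dosing on Day 14 with those that place a dose, or count the last dose, on Day 15. They fix the time since last dose for every off-drug sample.

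The cost is 15 more assays (30 with Day 29) and 4 mL more blood per subject (8 mL with Day 29). No visit or needle placement is added.

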#### 11.7 PHARMACOKINETIC ANALYSES

The PK analyses will include all subjects who received at least one dose of study drug and have sufficient plasma concentrations data for PK analysis.

EPN-701 plasma concentration will be measured at specific timepoints (see **Table 1**), tabulated and summarized by assessment time point. Descriptive statistics for plasma concentrations and PK parameters will include arithmetic means and SDs, geometric means and coefficients of variation, medians, and ranges, as appropriate.

In addition, depending on the plasma concentrations observed at the pre-specified time-points, the following PK parameters may be summarized using the same descriptive statistics as for plasma concentrations:

- Cmax [ng/mL]
- Tmax [hr]
- AUC0-24 [hr×ng/mL].

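### The 4-hour PK sample is drawn at the end of dialysis if that comes sooner, so a session under 3.5 hours puts it outside its own window and can miss the peak on Days 1 and 8

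*Combined protocol and SAP*

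**What the plan says.** Section 9.6.8.3 makes three statements about one sample.

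- The schedule for Days 1 and 8 lists it, after the 1, 2 and 3 h draws, as "4 hours (+/- 30 minutes)/before needle removal, 6 hours (+/- 30 minutes), 8 hours (+/- 30 minutes), and 24 hours (+/- 60 minutes) after study drug administration". A sample with the same 4 h ± 30 min tolerance is the only one after the 0-hour draw on Days 3, 5, 10, 12 and 15.
- The sequence rules say it is collected "when the dialysis is completed (before needle removal) or at 4 hours (+/- 30 minutes) after the 0-hour PK timepoint, whichever occurs first".
- A note says "The duration of dialysis sessions is expected to be approximately 4 hours" and adds that the "actual duration should not have an impact on the PK sample collection time-points".

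The same section fixes the clock: immediately "following drug administration, dialysis is to be started". It also requires actual clock times to be recorded and says the "actual elapsed time from dosing will be used for the PK calculations".

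Other sections describe the draw differently. The synopsis and note [14] to Table 1 give the 4 h window joined by a slash to needle removal, without the earlier-of-two rule. Section 8.1 places the post-dose samples during or at the end of dialysis. Sections 9.5.2 and 9.5.3 place this draw at the end of dialysis and give no clock time.

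For the analysis, Section 11.7 has concentrations "tabulated and summarized by assessment time point" and gives no rule for samples outside their window. Section 6.2.3 reports, from published data in healthy volunteers, that "maximum serum concentrations of MK-7 were seen approximately 4 hours after intake".

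**The concern.** A site cannot follow all three statements in Section 9.6.8.3 when a session is short. If it applies the earlier-of-two rule, session length decides the sampling time, which the note says should not happen, and the sample can fall before 3.5 h.

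Two things are at stake. First, Days 1 and 8 are the only days with a full profile, so they are the only days that can support Cmax, Tmax and AUC0-24. A draw pulled forward from 4 h thins the profile where the published data put the peak. Second, the by-time-point summary in Section 11.7 can pool samples taken at different times after the dose in one row. This is the first PK investigation of EPN-701 in humans and has 15 subjects, so a few thinned profiles would be visible in the summaries.

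**Working it through.** **Schedule check.** Scheduled PK samples per subject: 2 days × 8 + 5 days × 2 + 1 = 27. At about 4 mL each, 27 × 4 = 108 mL, which matches the volume in Section 9.6.8.3. Seven of the 27 are 4 h samples. Six of those fall on listed dosing days (Days 1, 3, 5, 8, 10, 12), or 6 × 15 = 90 across the study, of which 2 × 15 = 30 belong to full profiles.

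**Timing rule.** Dialysis starts right after the dose, so elapsed time at the end of dialysis is about the session length S. The rule gives sample time = min(S, 4 h), against a window of 3.5–4.5 h.

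| Session S | Sample drawn | In window? | Early by | Gap to nominal 6 h draw |
|---|---|---|---|---|
| 3.0 h | 3.0 h | No | 60 min | 3.0 h |
| 3.25 h | 3.25 h | No | 45 min | 2.75 h |
| 3.5 h | 3.5 h | Yes (limit) | 30 min | 2.5 h |
| 4.0 h or more | 4.0 h | Yes | 0 | 2.0 h |

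The conflict therefore begins exactly below 3.5 h. At 3.0 h the draw coincides with the scheduled 3 h draw. If a site instead follows Sections 9.5.2 and 9.5.3, which give only the end of dialysis, a session over 4.5 h also takes the sample out of its window.

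**Effect on Cmax (assumed profile).** The documents give no EPN-701 profile. Assume C(t) proportional to (t − L)·exp[−(t − L)/(4 − L)], which peaks at 4 h, with absorption lag L of 0, 1 or 2 h. With x = (t − L)/(4 − L), C(t)/C(4) = x·exp(1 − x).

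| Draw at | L = 0 | L = 1 | L = 2 | Shortfall against C(4) |
|---|---|---|---|---|
| 3.0 h | 0.96 | 0.93 | 0.82 | 4–18% |
| 3.25 h | 0.98 | 0.96 | 0.91 | 2–9% |
| 3.5 h | 0.99 | 0.98 | 0.96 | 1–4% |
| 6.0 h | 0.91 | 0.86 | 0.74 | — |

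Example, 3.0 h and L = 2: x = 1/2, and 0.5 × exp(0.5) = 0.82. With the 6 h draw on time, the early draw is the highest value observed for every L, so observed Cmax carries the shortfall and observed Tmax equals the time of that draw.

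**Second profile, and AUC.** A lagged absorption model with two-phase decline gives similar figures (peak at 4 h, lag 0–2 h, distribution rate 0.3–0.6 per h, assumed slow-phase weight 0.1, terminal half-life 68 h from Section 6.2.3). Observed Cmax is 0.83–0.97 of the 4 h value for a 3.0 h session and 0.91–0.99 at 3.25 h. Trapezoidal AUC0-24 on actual times, relative to the profile with the sample at 4 h, is 0.97–1.00 at 3.0 h and 0.985–0.998 at 3.25 h.

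**The case against.** The strongest reply is that the plan already limits the damage. Actual times are recorded and used in PK calculations, the 3 h and 6 h draws bracket 4 h on Days 1 and 8, sessions are expected to last about 4 h, and PK is exploratory, with parameters that only may be determined. The 4 h peak comes from healthy volunteers given MK-7, not from hemodialysis patients given 10 mg of EPN-701. All of this stands and keeps the point minor. It does not remove the contradiction: actual times cannot restore an observation that was not made, and bracketing a peak does not measure it.

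A reader might infer more than the documents support.

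- *That the sample is lost.* It is moved earlier; what is lost is an observation near 4 h.
- *That Cmax, Tmax or AUC are computed as if the draw were at 4 h.* Section 9.6.8.3 uses actual elapsed time, so the pooling risk is confined to the Section 11.7 summaries. Even there the row label is not stated and could be the combined one from the schedule.
- *That the 4–18% loss applies to every session under 3.5 h.* It belongs to a 3.0 h session.
- *That the error is systematic by patient.* The documents give no session-length distribution and nothing on variation within patients.
- *That the two-sample days lose Cmax and Tmax.* One post-dose sample cannot characterise either, whatever its timing; there the issue is only comparability in the summary table.
- *That Day 15 is simply another post-dose day.* The PK text describes dosing then, but Table 1 doses through Day 14 and Section 9.3.5 does not list Day 15.

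Figure 5, to which Section 9.6.8.3 refers for the sampling sequence, is not available here and could not be checked.

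**Conclusion.** The concern holds in a limited form. The timing rule in Section 9.6.8.3 contradicts both its own window and its own note once a session ends before 3.5 h, and other sections describe the same draw in further ways. On Days 1 and 8 the result can be an unobserved peak. Given a true peak at 4 h, a lag of 0–2 h and the 6 h draw on time, observed Cmax is low by about 4–18% for a 3.0 h session, falling to 1–4% near 3.5 h; AUC0-24 changes by at most about 3% in the cases examined. If the true peak lies elsewhere, these figures change. The number of subjects affected cannot be estimated and could be zero, because the plan gives neither a minimum session length nor a distribution. Severity is minor: PK is exploratory, all analyses are descriptive, and the primary safety endpoint is untouched.

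**What to change.** 1. **Days 1 and 8.** In Section 9.6.8.3 remove the earlier-of-two clause and require the sample at 4 h ± 30 min after dosing whether or not dialysis has ended, using the same access as the 6 h and 8 h draws.
2. **Days 3, 5, 10 and 12.** Keep the draw before needle removal, and limit the note on session duration so that it does not contradict this. In Section 11.7 state that only samples at 3.5–4.5 h actual elapsed time enter the 4 h summary, with the number contributing shown, and that the others are listed at their actual time.
3. **Consistency.** Carry the same wording into the synopsis, note [14] to Table 1, and Sections 8.1, 9.5.2 and 9.5.3, and check Figure 5 against it.
4. **Day 15.** Reconcile the PK text, which describes dosing on that day, with the Day 1–14 dosing schedule.

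The cost is wording. The total stays at 27 samples and 108 mL. The one practical downside is that a subject with a short session has the 4 h draw after needle removal on Days 1 and 8, when 6 h and 8 h draws are due anyway. On the other days, some 4 h rows may rest on fewer than 15 subjects.
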